Director, Division of Reproductive
Professor and Vice-chair Department of
Obstetrics, Gynecology and Reproductive
Sciences, Endocrinology and Infertility
Email: [contact]

Investigator

[name]
University of California San Francisco
Fellow in Reproductive Endocrinology &
Infertility
Email: [contact]

Synopsis

Primary Objective

To evaluate the impact of ovarian hyperstimulation on endometriosis-related symptoms.

Secondary Objectives (if applicable)

To evaluate the impact of letrozole use during ovarian hyperstimulation with respect to endometriosis-related symptoms, embryo/egg quality and quantity, and pregnancy rates.

Primary Outcome Variables

- To compare the mean endometriosis pain score at baseline and 6 and 12 weeks following egg retrieval.
- To evaluate how endometriosis pain scores change throughout controlled ovarian hyperstimulation.

Endometriosis associated symptoms will be evaluated using a survey modeled after the clinical survey developed by the World Endometriosis Research Foundation

Endometriosis Phenome and Biobanking Harmonisation Project. The survey will use a visual analog scale to quantify pain and symptoms experienced by participants.

Secondary and Exploratory Outcome Variables (if applicable)

- To compare the mean endometriosis pain score at baseline, 6 and 12 weeks following egg retrieval in the placebo, letrozole and control groups.
- To compare how endometriosis pain scores change throughout controlled ovarian hyperstimulation in the placebo, letrozole and control groups.
- To compare egg/embryo quantity and quality in the placebo, Letrozole and control groups.
- To compare follicular fluid estradiol levels between placebo, letrozole and control groups.
- To compare pregnancy rates in the placebo, Letrozole and control groups.

Study Duration

The total study duration will be approximately 12months. The total duration per participant will be approximately 14 weeks. Participants will be asked to take letrozole or placebo throughout their ovarian stimulation and for 2 weeks following retrieval. Participants will be asked to complete surveys up to 12 weeks following retrieval.

Study Design

Randomized double blinded placebo-controlled trial. There will be a total of 60 participants, with 20 participants with endometriosis randomized to the placebo group, 20 participants with endometriosis randomized to the letrozole group and 20 control patients with no history of endometriosis. Letrozole and placebo medication will be started on the first day of gonadotropin injections and continued until the day of trigger shot. Medication will be restarted the night of egg retrieval and continued for 2 weeks post retrieval. Endometriosis associated symptoms will be evaluated using a survey modeled after the clinical survey developed by the World Endometriosis Research Foundation Endometriosis Phenome and Biobanking Harmonisation Project. Surveys will be administered at baseline ultrasound appointment for controlled ovarian hyperstimulation cycle, the day of trigger shot, 3 weeks following egg retrieval, 6 weeks following egg retrieval and 12 weeks following egg retrieval.

Study Population

Reproductive age women with a prior diagnosis of endometriosis, who are undergoing controlled ovarian stimulation.

Number of Participants

A total of 60 participants (20 in each of the primary comparison groups) as well as an additional 20 age matched controls without a history of endometriosis will be enrolled. Enrollment will occur over a 12-month period, from April 2019 to April 2020.

Number of Study Sites

There is a single study site for this trial. All participants will be recruited, and all study related activities will be completed, at the University of California San Francisco Center for Reproductive Health.

Table of Contents

1 - Introduction	10
1.1 Introductory Statement	10
2 - Background	11
2.1.1 Preclinical Experience.....	11
2.1.2 Clinical Experience.....	11
2.2 Background/prevalence of research topic	11
3 - Rationale/Significance.....	12
3.1 Problem Statement.....	12
3.2 Purpose of Study/Potential Impact	12
3.3.1 Potential Risks	12
3.3.2 Potential Benefits	13
4 - Study Objectives	14
4.1 Hypothesis	14
4.2 Primary Objective	14
4.3 Secondary Objectives (if applicable)	14
5 - Study Design.....	15
5.1 General Design Description.....	15
5.1.1 Study Date Range and Duration	15
5.1.2 Number of Study Sites	15
5.2.1 Primary Outcome Variables	15
5.2.2 Secondary and Exploratory Outcome Variables (if applicable).....	15
5.3 Study Population.....	15
5.3.1 Number of Participants.....	16
5.3.2 Eligibility Criteria/Vulnerable Populations.....	16
6 - Methods	17

1.1 Introductory Statement

Endometriosis is an estrogen dependent disease present in 25-35% of infertile women. Given controlled ovarian hyperstimulation leads to a considerable rise in serum estradiol concentrations, patients and providers must consider the possible risk of disease and symptom progression related to controlled ovarian hyperstimulation. Aromatase inhibitors, such as Letrozole, markedly suppress plasma estrogen levels and are commonly used during controlled ovarian hyperstimulation in cancer patients with estrogen-sensitive cancers. It is therefore reasonable to investigate the benefit of using letrozole during controlled ovarian hyperstimulation in patients previously diagnosed with endometriosis.

2 - Background

2.1.1 Preclinical Experience

See Clinical Experience below in section 2.1.2 (below).

2.1.2 Clinical Experience

Aromatase inhibitors, such as letrozole, markedly suppress plasma estrogen levels by competitively inhibiting the activity of the aromatase enzyme and are effective in treating endometriosis related pain [1-4]. Letrozole is FDA approved for use in cancer patients with estrogen-sensitive cancer undergoing fertility preservation. The addition of letrozole has been shown to decrease serum estradiol levels closer to that observed in natural cycles (i.e., E2 <500 pg/mL) without affecting oocyte or embryo yield [5, 6]. It is therefore reasonable to consider the use of letrozole during controlled ovarian hyperstimulation in patients with endometriosis, with a goal of minimizing any impact on patient symptoms. Additionally, given improved pregnancy outcomes following suppression of endometriosis with GnRH agonists, letrozole suppression of endometriosis during controlled ovarian hyperstimulation may improve cycle outcomes in patients with endometriosis.

2.2 Background/prevalence of research topic

Endometriosis is an estrogen dependent disease present in 25-35% of infertile women. Given controlled ovarian hyperstimulation leads to development of multiple follicles and considerable rise in serum estradiol concentrations, patients and providers must consider the possible risk of disease and symptom progression related to controlled ovarian hyperstimulation. This may be especially true with repeated stimulations.

With respect to disease progression, data have been contradictory, but overall favor that there is no significant risk of disease progression with controlled ovarian hyperstimulation. The impact of controlled ovarian hyperstimulation on endometriosis related symptoms is less clear, with a single prospective cohort study of 64 patients with endometriosis, published in 2011, showing no marked worsening in symptoms [7]. Study limitations include lack of a control group, small sample size and a limited follow-up time of 3-6 months. Anecdotally, providers from our institution's Center for Reproductive Health and Center for Endometriosis do feel patients often report a flare in endometriosis related symptoms following controlled ovarian hyperstimulation. Overall, the question remains open and further investigation is warranted.

Additionally, the impact of endometriosis on in vitro fertilization outcomes has been a long-debated topic, with some studies showing poorer outcomes compared to controls and others showing no impact. Prolonged use of a GnRH agonist before in vitro fertilization with embryo transfer, in patients with endometriosis, has been associated with significantly higher ongoing pregnancy rates [8, 9].

3 - Rationale/Significance

3.1 Problem Statement

Endometriosis is an estrogen dependent disease commonly present in infertile women. Controlled ovarian hyperstimulation is a common treatment for infertility, however results in a considerable rise in serum estradiol concentrations. Given this, it is important for patients and providers to consider and minimize the possible risk of disease and symptom progression related to controlled ovarian hyperstimulation.

3.2 Purpose of Study/Potential Impact

Given the high prevalence of endometriosis among infertile women, optimizing the management of symptoms during controlled ovarian hyperstimulation in this patient population is a challenge faced by all clinical reproductive endocrinologists. Currently there are no evidence-based recommendations to improve patient experience or ovarian simulation outcomes in this patient population.

Letrozole is an aromatase inhibitor that markedly suppresses plasma estrogen levels by competitively inhibiting the activity of the aromatase enzyme. It has previously been shown to be an effective treatment for endometriosis related pain outside of controlled ovarian hyperstimulation. Letrozole, is regularly used in cancer patients with estrogen-sensitive cancer undergoing controlled ovarian hyperstimulation for fertility preservation.

This trial could provide evidence for the use of Letrozole in patients with endometriosis. This would be a relatively low cost, minimally invasive, intervention for this patient population. Further, it would be the first evidence-based recommendation to improve patient experience and/or ovarian simulation outcomes in this patient population.

3.3.1 Potential Risks

Risks and side effects related to the possible use of Letrozole include those which are:

Likely

- Flushing
- Mood changes
- Hot flushes
- Bloating

Less Likely

- Headache
- Fatigue
- Insomnia

Rare but serious

- Headache with vision changes

- Blood clot

Patients undergoing controlled ovarian hyperstimulation are monitored every 1-3 days by University of California Center for Reproductive Health providers. During this monitoring patients will be assessed for any possible concerns or side effects of the study medication. All concerns will be recorded and reviewed by the Data Safety and Monitoring Board on a monthly basis.

3.3.2 Potential Benefits

Taking part in this study may or may not make participants health better. If letrozole proves to be better than the placebo group, this group may benefit from participating in the study, but this cannot be guaranteed. Information gained from this study will help improve the IVF process for future patients, particularly patients with endometriosis.

In return for the time and effort participants put into completing the study surveys, they will be paid \$60 in compensation. They will received \$30 after the completion of survey two and an additional \$30 at the completion of survey 5.

4 - Study Objectives

4.1 Hypothesis

Null hypotheses:

- a) Ovarian hyperstimulation has no impact on endometriosis-related symptoms.
- b) The use of letrozole during ovarian hyperstimulation has no impact on endometriosis-related symptoms.
- c) The use of letrozole during ovarian hyperstimulation has no impact on egg/embryo quantity or quality.
- d) The use of letrozole during ovarian hyperstimulation has no impact on pregnancy rates.

4.2 Primary Objective

To evaluate the impact of ovarian hyperstimulation on endometriosis-related symptoms.

4.3 Secondary Objectives (if applicable)

To evaluate the impact of letrozole use during ovarian hyperstimulation with respect to endometriosis-related symptoms, embryo/egg quality and quantity and pregnancy rates.

5 - Study Design

5.1 General Design Description

Randomized double blinded placebo-controlled trial.

5.1.1 Study Date Range and Duration

We anticipate it will take 12 months to enroll and complete this study. Enrollment is scheduled to begin in April of 2019 and conclude by April 2020.

The total duration per participant will be approximately 14 weeks. Participants will be asked to take letrozole or placebo throughout their ovarian stimulation and for 2 weeks following their retrieval. Participants will also be asked to complete surveys up to 12 weeks following their retrieval. Ovarian follicular fluid will be obtained at the time of egg retrieval for hormonal evaluation.

The study will involve long-term follow-up, including periodic review of participant medical records to evaluate future treatments received to treat their endometriosis and evaluate the use and outcomes of the eggs/embryos preserved during their ovarian stimulation cycle.

5.1.2 Number of Study Sites

There is a single study site for this trial. All participants will be recruited, and all study related activities will be completed, at the University of California San Francisco Center for Reproductive Health.

5.2.1 Primary Outcome Variables

- To compare the mean endometriosis pain score at baseline, 6 and 12 weeks following egg retrieval.
- To evaluate how endometriosis pain scores change throughout controlled ovarian hyperstimulation.

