5.2.2 Secondary and Exploratory Outcome Variables (if applicable)

- To compare the mean endometriosis pain score at baseline, 6 and 12 weeks following egg retrieval in the placebo, letrozole and control groups.
- To compare how endometriosis pain scores change throughout controlled ovarian hyperstimulation in the placebo, letrozole and control groups.
- To compare egg/embryo quantity and quality in the placebo, letrozole and control groups. This will include evaluation of: total oocyte yield per starting antral follicle count, total mature oocyte yield per oocytes collected, embryo yield per starting antral follicle count, embryo yield per oocyte retrieved, fertilization rate per mature oocyte retrieved, ovarian follicular fluid hormone levels.
- To compare pregnancy rates per embryo transfer in the placebo, letrozole and control groups.

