6.4.1 Statistical Design

An intention-to-treat analysis of the results will be used, meaning results of the study will be based on the initial treatment assignment and not the treatment eventually received. The primary outcome will be assessed by changes in pain survey scores before, during and following controlled ovarian hyperstimulation.

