6.4.2 Sample Size Considerations

Primary Outcome: change in endometriosis-related pain score pre and post controlled ovarian hyperstimulation.

Test: two sample test.

1:1 randomization powered at 0.9 to detect a 3-point difference on the VAS pain scale.

A standard deviation of 2.5 was used, based on previous literature [11].

The effect size of 3 was based on review of the literature which supports the most accurate evaluation of endometriosis related pain using a visual acuity scale. Using this scale, a change in 3 points typically results in change in pain category (mild, moderate, severe) and therefore represents a clinically significant reduction or increase in symptoms.

Sample Size Estimate: A total of 40 participants (20 in each of the primary comparison groups) would provide 90% power to detect a change in pain score of 3 between the two groups. This accounts for an estimated study participant dropout rate of 20%.

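### No primary analysis estimates what hyperstimulation itself does to symptoms: the primary outcome names no group, and the only test specified compares letrozole with placebo

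*Combined protocol and SAP*

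**What the plan says.** The primary objective (4.2) is "To evaluate the impact of ovarian hyperstimulation on endometriosis-related symptoms". Null hypothesis (a) in 4.1 has the same subject. The effect of letrozole on symptoms is null hypothesis (b) and a secondary objective (4.3).

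The first primary outcome in 5.2.1 is "To compare the mean endometriosis pain score at baseline, 6 and 12 weeks following egg retrieval". The second is the course of pain scores during stimulation. Neither names a group. Section 6.4.1 is equally silent: "The primary outcome will be assessed by changes in pain survey scores before, during and following controlled ovarian hyperstimulation". So is the outcome line in 6.4.2: "change in endometriosis-related pain score pre and post controlled ovarian hyperstimulation".

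The groups appear only one level down. The first secondary outcome in 5.2.2, repeated in 6.4.3.2, is "To compare the mean endometriosis pain score at baseline, 6 and 12 weeks following egg retrieval in the placebo, letrozole and control groups".

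The tests point elsewhere. Section 6.4.2 sizes the trial with a two-sample test between two groups of 20, and 6.4.3.1 gives a two-sample t-test or rank sum test for pain scores. No paired, one-sample or longitudinal method is named.

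Half of the 40 women with endometriosis are randomised to letrozole (5.3.1), taken during stimulation and for 2 weeks after retrieval (6.1.2). Of aromatase inhibitors such as letrozole, section 2.1.2 says they "are effective in treating endometriosis related pain".

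**The concern.** A primary result should estimate the quantity the primary objective asks about. Here the outcome wording and the test wording lead to two different quantities, and neither is the effect of stimulation.

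If the before-after change is taken over all women with endometriosis, it averages stimulation alone with stimulation plus a drug the protocol regards as active against this pain. The better letrozole works, the closer that average moves towards no impact. If the two-sample test is taken as the primary analysis, it isolates letrozole, and stimulation, which both arms receive, cancels out.

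This matters because section 2.2 treats the question as open and reports the local impression that "patients often report a flare in endometriosis related symptoms following controlled ovarian hyperstimulation". An attenuated primary estimate could be used to reassure women having ordinary stimulation without letrozole.

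**Working it through.** **The plan's own figure.** Inputs from 6.4.2: difference 3 points, SD 2.5, power 0.90, 20% dropout. Alpha is 0.05 from 6.4.3.1, taken as two-sided because sidedness is not stated. The normal approximation gives 2 × (2.5 × (1.960 + 1.282) / 3)² = 14.6, so 15 per arm. The exact two-sample t-test has power 0.907 with 16 per arm, and 16 / (1 − 0.2) = 20. The stated 20 per arm reproduces, but as a between-arm comparison. It does not size a before-after change.

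**What a pooled change estimates.** Let d be the true mean change on placebo and L the amount by which letrozole lowers the change. With equal arms:

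pooled change = [d + (d − L)] / 2 = d − L/2

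- Letrozole halves the flare (L = d/2): pooled = 0.75 d.
- Letrozole abolishes the flare (L = d): pooled = 0.50 d.
- Letrozole does nothing (L = 0): pooled = d.

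If the wording also admits the 20 controls and they do not change, an abolished flare gives (d + 0 + 0) / 3 = 0.33 d.

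**Power.** Assumptions: 20% dropout, leaving 16 placebo completers or 32 over both arms; one change score at one time point; one-sample t-test at two-sided 0.05; within-arm SD of change 2.5. Section 6.4.2 does not say whether its 2.5 is the SD of a score or of a change. For the pooled analysis the between-arm spread is added: SD = √(2.5² + (L/2)²). For d = 2, L = 2 this is √(6.25 + 1) = 2.69.

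| True flare on placebo | Placebo arm alone (n = 16) | Pooled (n = 32), letrozole has no effect | Pooled, letrozole halves flare | Pooled, letrozole abolishes flare |
|---|---|---|---|---|
| 3 points | 0.99 | above 0.99 | above 0.99 | 0.81 |
| 2 points | 0.85 | 0.99 | 0.90 | 0.53 |
| 1.5 points | 0.61 | 0.91 | 0.68 | 0.35 |

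When letrozole halves the flare, pooled power is no lower than placebo-arm power, because doubling n outweighs the 25% attenuation. The estimate is still biased. Power is lost in the column where the flare is abolished.

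**Sensitivity to the SD of change.** If 2.5 is the SD of a score, the SD of change is 2.5 × √(2(1 − r)), where r is an assumed within-person correlation: 2.96 at r = 0.3, 2.50 at r = 0.5 and 1.94 at r = 0.7. For a 2-point flare, placebo-arm power is then 0.72, 0.85 and 0.97. Pooled power with the flare abolished is 0.42, 0.53 and 0.71.

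**Precision.** 95% CI half-width = t × SD / √n. For n = 16: 2.131 × 2.5 / 4 = 1.33. For n = 32 at the same SD: 2.040 × 2.5 / 5.657 = 0.90.

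**The case against.** The strongest reply is that pooling is inferred. No section prescribes a pooled mean change, and where the analysis becomes operational (6.4.2, 6.4.3.1) it compares two arms, analysed as randomised (6.4.1). This stands: a reader should not conclude that the plan states it will average in the letrozole women. But it does not rescue the plan. The between-arm test answers hypothesis (b) and leaves the primary objective with no primary analysis.

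Second, the size of the dilution depends on a letrozole effect the documents do not give. The 3 points in 6.4.2 is justified as a clinically relevant change, not as an expected drug effect. Study drug also stops 2 weeks after retrieval, so any effect at 6 and 12 weeks, which is 4 and 10 weeks off drug, may be smaller. This stands for the first primary outcome. It has less force for the second, because the trigger-day survey (6.2) follows daily dosing.

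A reader might infer that a real flare would be wiped out, with power at the 5% false-positive rate. For a 1.5-point flare, that requires letrozole to take pain 1.5 points below baseline (L = 3), beyond preventing the flare. Nothing in the documents supports that as the expected case.

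Third, placebo-arm means at the same times are prespecified as secondary (5.2.2, 6.4.3.2). This also stands: a flare would be displaced from the primary result but not lost from the report.

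**Conclusion.** The point holds. The primary objective has no matching primary analysis under either reading of the plan: the literal outcome mixes stimulation with and without letrozole, and the specified test estimates the letrozole effect.

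The robust harm of the literal reading is an attenuated estimate, at 75% or 50% of the placebo-arm change if letrozole halves or abolishes the flare in equal arms. Loss of power is conditional: 0.53 against 0.85 for an abolished 2-point flare, and none if the flare is only halved. These figures rest on an assumed SD of change of 2.5, 20% dropout, a two-sided test and assumed letrozole effects. If letrozole has no effect on pain, pooling the two endometriosis arms introduces no bias, but a primary outcome should not depend on the trial drug failing.

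**What to change.** - **Synopsis, 5.2.1 and 6.4.1:** define the primary outcome as the within-person change in pain score from baseline in women with endometriosis randomised to placebo.
- **6.4.2 and 6.4.3.1:** name a paired or longitudinal test for that change and restate its power. With 16 completers of 20 and SD of change 2.5, power is about 0.99 for 3 points, 0.85 for 2 and 0.61 for 1.5. Say whether 2.5 is the SD of a score or of a change.
- **Hypothesis (b):** keep letrozole versus placebo, two-sample, 20 per arm, as its named comparison. The existing sample size calculation belongs there.
- **Controls:** show the change in women without endometriosis alongside, as context.
- **Pooled change:** if reported at all, label it descriptive.

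This needs no new patients or data, but it is more than a wording change, since the test and the power statement must change too. The cost is precision: the 95% CI half-width is about 1.3 points instead of 0.9. The placebo-arm change also does not isolate stimulation. It still contains placebo response and natural fluctuation in pain, with baseline typically taken on cycle day 2 (6.3.5). The protocol should state this as a limitation, especially as section 2.2 faults the earlier cohort for having no control group.

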6.1.2 Dosage, Admin, Schedule (if applicable)

Whether placed into the intervention, placebo or control group, all participants will receive their usual gonadotropin injections and trigger shot for their controlled ovarian hyperstimulation cycle, as standardly prescribed by their primary provider at the University of California Center for Reproductive health. In addition:

- The intervention group will receive oral letrozole 5 mg per day, starting on the first day of gonadotropin injections and continued until the day of trigger shot. Oral letrozole 5mg per day will be then be restarted the night of egg retrieval and continued for 2 weeks post retrieval.
- The placebo group will receive oral placebo, starting on the first day of gonadotropin injections and continued until the day of trigger shot. Daily oral placebo will be restarted the night of egg retrieval and continued for 2 weeks post retrieval.

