6.4.3.2 Secondary Objectives Analyses

For our secondary outcomes, we will be evaluating the outcomes of the placebo and letrozole groups. Specifically, this will include:

- Comparison of the mean endometriosis pain score at baseline, 6 and 12 weeks following egg retrieval in the placebo, letrozole and control groups.
- Comparison of how endometriosis pain scores change throughout controlled ovarian hyperstimulation in the placebo, letrozole and control groups.
- Comparison of egg/embryo quantity and quality in the placebo, letrozole and control groups. This will include evaluation of: total oocyte yield per starting antral follicle count, total mature oocyte yield per oocytes collected, embryo yield per starting antral follicle count, embryo yield per oocyte retrieved, fertilization rate per mature oocyte retrieved, follicular fluid hormone levels.
- Comparison of pregnancy rates per embryo transfer in the placebo, letrozole and control groups.

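### No dated pain comparison names the 3-week survey, so the period from retrieval to week 6 has data but no specified analysis

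*Combined protocol and SAP*

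**What the plan says.** **Treatment.** Letrozole or placebo runs from the first gonadotropin day until trigger, restarts on the night of retrieval and is "continued for 2 weeks post retrieval" (6.1.2).

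**Surveys.** Pain is recorded at baseline and then on "the day of trigger shot, 3 weeks following egg retrieval, 6 weeks following egg retrieval and 12 weeks following egg retrieval" (Synopsis, Study Design; also 6.2 and 6.3.1). Section 6.3.5 adds a telephone reminder for each of the three post-retrieval surveys.

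**Dated comparisons.** The first primary outcome in 5.2.1 is "To compare the mean endometriosis pain score at baseline, 6 and 12 weeks following egg retrieval". The between-group version in 5.2.2 is "To compare the mean endometriosis pain score at baseline, 6 and 12 weeks following egg retrieval in the placebo, letrozole and control groups", and 6.4.3.2 repeats it: "Comparison of the mean endometriosis pain score at baseline, 6 and 12 weeks following egg retrieval in the placebo, letrozole and control groups". The synopsis lists match. None names 3 weeks.

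**Undated comparisons.** Section 5.2.1 has a second primary outcome, "To evaluate how endometriosis pain scores change throughout controlled ovarian hyperstimulation", and 5.2.2 has its between-group counterpart, "To compare how endometriosis pain scores change throughout controlled ovarian hyperstimulation in the placebo, letrozole and control groups". Section 6.4.1 adds: "The primary outcome will be assessed by changes in pain survey scores before, during and following controlled ovarian hyperstimulation". None of these gives a week.

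**The concern.** The 3-week survey is scheduled, participants are telephoned to complete it, and it is the first pain measure after the whole course of study drug. Followed as written, the dated comparisons leave it out. The omission recurs in the synopsis, 5.2.1, 5.2.2 and 6.4.3.2, so it does not look like a slip in one place.

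This matters because of the trial's own motivation. Section 2.2 cites clinicians' impression that symptoms often flare after stimulation, and null hypothesis (b) in 4.1 concerns letrozole's effect on symptoms. If a flare, or its prevention by letrozole, arose after retrieval and settled before week 6, the dated comparisons could report no impact. If the 3-week score were brought in only after the data had been seen, it would be a post hoc choice.

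**Working it through.** **1. Timing.** Time since last capsule = survey week − 2, both counted from retrieval.

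| Survey | Weeks since last capsule | Named in a dated comparison |
|---|---|---|
| 3 weeks | 3 − 2 = 1 | No |
| 6 weeks | 6 − 2 = 4 | Yes |
| 12 weeks | 12 − 2 = 10 | Yes |

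The baseline and trigger-day surveys bracket stimulation and serve the outcome on change during stimulation. The only survey between retrieval and week 6, a period that includes the 2-week post-retrieval drug course, is the one at 3 weeks.

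**2. The plan's own sample size.** Inputs from 6.4.2: difference 3 points, SD 2.5, power 0.90, dropout 20%. Level 0.05 from 6.4.3.1; two-sided is assumed because sidedness is not stated. Standardised difference = 3/2.5 = 1.2. A two-sample t-test needs 15.62, so 16 per arm, and 16/0.8 = 20 per arm. The stated figure reproduces. With 16 completers per arm, power for 3 points is 90.7%.

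**3. Illustration of a fading effect.** The documents give no rate of decay, so the half-life h is an assumption. Take a letrozole-placebo difference of 3 points at week 3. The difference at week w is 3 × 0.5^((w − 3)/h). Power uses the same t-test, SD 2.5 and 16 per arm.

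| Assumed half-life | Difference at week 6 | Power at week 6 |
|---|---|---|
| 2 weeks | 3 × 0.5^(3/2) = 1.06 | 21% |
| 4 weeks | 3 × 0.5^(3/4) = 1.78 | 50% |
| 8 weeks | 3 × 0.5^(3/8) = 2.31 | 72% |
| 12 weeks | 3 × 0.5^(3/12) = 2.52 | 79% |

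Without a half-life, by the share of the 3 points still present when measured: 75% (2.25 points) gives 69% power, 50% (1.5 points) gives 38%, and 25% (0.75 points) gives 13%.

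**The case against.** The strongest reply is that most of the early period is already covered. Survey #2 is taken on trigger day, at the end of the stimulation course of study drug, and the outcome on change during stimulation uses it, as a primary outcome and again by group. A reader might infer from the dated lists that the plan looks only at 6 and 12 weeks and would miss any early effect. The documents do not support that: an on-drug effect or a flare present by trigger day falls within a listed comparison. This part of the reply stands and confines the point to retrieval to week 6.

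A reader might also infer that the 3-week data will go unused. That is too firm. The reference in 6.4.1 to scores after stimulation excludes no week, and 6.3 introduces the surveys as taking place during stimulation although three of the five follow retrieval, so the undated outcomes may be meant broadly. What the text supports is that no dated comparison names the survey. The vagueness does not settle the matter: 6.4.2 says only pre and post, and 6.4.3.1 gives a two-sample test without a time point, so an analyst cannot tell whether week 3 counts.

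Third, weeks 6 and 12 are a defensible choice. The background is concerned with symptom progression and criticises the earlier cohort for limited follow-up. The reported flare is anecdotal, and nothing says that it fades before week 6. This stands as a reason to leave the primary time points alone. It gives no reason to leave a collected survey without a stated role.

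**Conclusion.** The point holds as a limited gap in specification. Any flare or letrozole effect confined to the weeks between retrieval and week 6 would be visible only in survey #3, to which the plan assigns no dated comparison.

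Its size cannot be derived from the documents. The week-6 power range of 21% to 79% depends on the assumed half-life, on a full 3-point difference at week 3, and on the plan's SD and dropout applying at both weeks. It concerns the letrozole-placebo contrast, which is a secondary objective (4.3). It should not be read as a forecast, nor as evidence that the chosen primary time points are wrong. This is a worthwhile low-cost improvement, not a flaw that threatens the trial.

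**What to change.** 1. Add 3 weeks to the secondary pain time points in 5.2.2, in 6.4.3.2 and in the matching synopsis list.
2. State in 6.4.3.2 that the letrozole-placebo differences at trigger, 3, 6 and 12 weeks will be estimated from one baseline-adjusted repeated-measures model using all surveys, and reported with confidence intervals.
3. Leave the primary time points as the sponsor has set them.

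The cost is wording only: no new visits, data or participants. The downside is one more secondary contrast, to be reported without a confirmatory claim. Adding the time point alone would close the gap in the lists; the single model also avoids a separate two-sample test at each survey.
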